1.4 Anticipated duration of the clinical investigation

The total duration of the clinical investigation is expected to be approximately 4 weeks: 2 weeks randomized to one arm of the study and 2 additional weeks with access to both websites.

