Research website – Participants will be introduced to the research website during the baseline session (V1). The research website is a portal that will contain links to two interventions including ToT and an attention control (unos.org). Before accessing the research website during the baseline session, participants will be randomized to first receive access to only one of the two websites through the portal. The research website will track website usage (i.e. time spent, content accessed, etc.) for all study participants for both ToT and unos.org. Once the participant completes the 2-week study visit (V2), the portal will contain access to both ToT and unos.org for the remainder of the study (2 more weeks).

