2.5.3 Allocation to treatment arms

Participants will be randomized 1:1 to either the intervention (“Take on Transplant”) or the attention control (unos.org), stratified by $FEV_1 < 30\%$ versus 30-50%. Participants will be given access to their assigned website via the research website portal for two weeks. After the 2-week session interview, access to the opposite arm assignment will be unlocked and participants will have unlimited access to both the intervention (ToT) and the attention control (Unos.org).

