- GAD-7 is a scale that measures symptoms of anxiety in the prior 2 weeks on a 0-21 scale, with higher scores indicating worsening anxiety and a score of 10 or higher consistent with a diagnosis of generalized anxiety disorder. Investigators will assess the difference in mean GAD-7 score in the intervention versus control arms of the study at the 2-week study visit. Investigators will also determine the proportion with new GAD-7 score greater than or equal to 10 in each arm.
- Longitudinally characterize time spent using Take on Transplant through analysis of patient-level usage data. Average time spent using the research website from baseline to 2 weeks will be compared across study arms. Further, time spent using the investigator-designed website will be assessed as a predictor of: 1. change in CTF knowledge about LTx (14-question investigator-designed survey) from baseline to 2-week study visit, 2. change in Likert preparedness from baseline to 2-week study visit, 3. change in Decisional Conflict Scale from baseline to 2-week study visit, and 4. mean PrepDM Scale at 2-weeks.
- The PrepDM Scale will be measured for all participants with respect to Take on Transplant and mean score will be compared for participants in the intervention (4 weeks of exposure) versus control arms (2 weeks of exposure). PrepDM scores range on a scale from 0 to 100 with higher scores indicating a higher perceived level of preparation for decision making.
- Identify baseline demographic and health literacy predictors of increased tool usage.

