2.6.3 Statistical analysis plan

Primary endpoints

The co-primary endpoint is feasibility, which will be defined successful by 90% of enrolled participants completing the 2-week study visit (V2). Descriptive statistics will be used to determine whether this threshold was met.

The co-primary endpoint of difference in PrepDM scale score (Difference = intervention – control) at 2-weeks will be assessed using linear regression, with statistical significance level set at 2-sided alpha <0.05.

Secondary endpoints

Continuous secondary endpoints will be assessed using linear regression, with statistical significance level set at 2-sided alpha <0.05.

Categorical secondary endpoints will be assessed using Pearson's chi-squared test of independence, with statistical significance level set at 2-sided alpha <0.05.

Graphical methods and descriptive statistics will be used to evaluate differences in usage during the 4 weeks of access across subsets of the cohort with different socioeconomic

status (based on insurance status, income, education level) and health literacy (based on S-TOFHLA). Exploratory models will test for a dose-response relationship by 1) time spent using the tool (uses/week) and 2) number of ‘CF Stories’ viewed and PrepDM Scale at 2-week and 4-week study visits. Linear regression may be used to determine whether predictors of increased time spent using the tool can be identified from baseline demographics and questionnaire results. Subgroup analyses will compare changes across instruments among participants with adequate health literacy to those with inadequate or marginal health literacy. We will also perform subgroup analysis for patients with $FEV_1 < 30\%$ predicted.

These data will inform the feasibility of completing a larger, multicenter, randomized controlled trial of ToT and will inform duration of the larger trial.

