3. Was there anything that prevented you from using the website? If yes, can you walk me through them in more detail and discuss ways they could be addressed?
4. Can you tell me about any technical issues you may have experienced with the website or devices?
5. How satisfied are you with the amount of time you spent visiting the site over the past two weeks? Do you think there could be any value in returning at another time? What would you spend more time looking at? What might prompt you to return to the website again?
6. Now can you tell me some of your general opinions about the website? Why was or wasn't it engaging?
7. Can you give me an example of some topics you enjoyed reading about or topics you might have preferred to avoid?
8. Can you give me an example of information you might have found surprising? Why was it surprising to you?
9. How did the content in the website make you feel?
10. Do you think this website would be a good place to start your search for information about lung transplant for CF? Why or why not? Describe the questions about lung transplant that still remain after your use of this website.
11. Why might you recommend this website to others or not?
12. Do you think this would be a good website for your doctor to recommend?
13. Imagine you have an appointment tomorrow with your CF doctor, how prepared do you feel to discuss lung transplant after using this website? Why? (consider asking: why not [lower on Likert scale]? why not [higher on Likert scale]?)
14. How might you benefit from using the website with others (e.g. your doctor, friend, family)? Did you share any of the information on the website with others? If yes, what did you discuss?

Week 4 - 60 minute session

Goals of interview:

- Feasibility of use
- Preparedness for CF clinic visit
- Psychological impact
- Duration of RCT (4 weeks vs 3 months)

1. Can you tell me about how often you looked at the website over the past two weeks? Was there anything that prevented you from using the website, technical issues or something else? If yes, can you walk me through them in more detail and discuss ways they could be addressed?

2. How satisfied are you with the amount of time you spent visiting the sites over the past four weeks? Do you think there could be any value in returning to either site at another time? What would you spend more time looking at? What might prompt you to return to the websites again?

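### The week-4 PrepDM comparison is labelled by exposure time, but it compares two access sequences and cannot isolate the effect of longer Take on Transplant access

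*Combined protocol and SAP*

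**What the plan says.** The relevant text is spread over several sections of the combined protocol and SAP.

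- **Endpoint (2.6.1).** "The PrepDM Scale will be measured for all participants with respect to Take on Transplant", and the "mean score will be compared for participants in the intervention (4 weeks of exposure) versus control arms (2 weeks of exposure"). The visit is not named.
- **Allocation and first period (2.5.3, 2.5.2).** "Participants will be randomized 1:1 to either the intervention" or the attention control, unos.org, and "participants will be randomized to first receive access to only one of the two websites through the portal".
- **Second period (2.5.3, 1.4).** After the 2-week session, "access to the opposite arm assignment will be unlocked and participants will have unlimited access to both" sites. The calendar is "2 weeks randomized to one arm of the study and 2 additional weeks with access to both websites".
- **Analysis (2.6.3).** Continuous secondary endpoints are analysed by linear regression at two-sided 0.05. No order, sequence or carry-over effect is mentioned. Exploratory models relate observed usage to PrepDM at the 2-week and 4-week visits, again with no order adjustment named.
- **Use of the results (2.6.3, Appendix 1).** The data "will inform duration of the larger trial". One listed goal of the week-4 interview is "Duration of RCT (4 weeks vs 3 months").

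**The concern.** The endpoint labels the two arms by weeks of ToT access, as if that were what separates them at V3. It is one of several differences. Intervention participants met ToT first and had unos.org added later. Control participants spent two weeks on a general all-organ site, were interviewed about it, and met ToT second. PrepDM is rated with respect to a named tool, so an earlier tool could shift the score in either direction. ToT might be rated higher by contrast with a less specific site, or lower because some questions had already been answered.

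What is at stake is the choice of access period for the larger trial. This is the plan's only randomized contrast of exposure length. A positive difference could be due to order alone. A null difference could hide a real gain from longer access that an opposite order effect cancels.

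**Working it through.** **Plan's own figure.** No figure is given for this comparison. The only computed figure in section 2.6.2 is the interval for 90% completion of the 2-week visit among 50 enrolled. A Wilson interval for 45/50 gives 78.6% to 95.7%, which matches the stated 79-96%. The 45 completers (about 22 or 23 per arm) are used below for V3 as well. The plan gives no V3 completion rate, so this is an assumption.

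**Step 1: identify the visit.** ToT access of 4 weeks in one arm and 2 weeks in the other occurs only at V3.

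**Step 2: set out the two arms at V3.**

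| | Intervention | Control |
|---|---|---|
| Weeks of ToT access | 4 | 2 |
| Weeks of unos.org access | 2 | 4 |
| ToT accessed first (1 = yes) | 1 | 0 |
| ToT rated before on PrepDM (1 = yes) | 1 | 0 |

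The last row is inferred: ToT was the intervention arm's only site when PrepDM was completed at the 2-week visit (V2). All weeks are weeks of access, not of measured use.

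**Step 3: what the arm difference estimates.** Let a be the effect per week of ToT access, b the effect per week of unos.org access, c the effect of having ToT first, and d the effect of a prior rating. Then

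intervention − control at V3 = (4 − 2)a + (2 − 4)b + c + d = 2a − 2b + c + d.

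The design matrix with intercept, ToT weeks and order has rank 2 for 3 columns. Adding unos.org weeks and prior rating leaves it at rank 2 for 5 columns. Only the sum is estimable, and no regression on the V3 arm contrast alone can divide it.

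**Step 4: illustration in assumed SD units.** Simulation with 23 versus 22 completers, 20,000 replicates, two-sided 0.05:

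| Total duration effect | Order effect | Mean arm difference | Significant |
|---|---|---|---|
| 0 | +0.5 SD | 0.50 SD | 37% |
| +0.5 SD | 0 | 0.50 SD | 37% |
| +0.5 SD | −0.5 SD | 0.00 SD | 5% |

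The first two rows cannot be told apart from the data. With no duration effect, order effects of 0.2, 0.3, 0.5 and 0.8 SD would be significant in about 10%, 17%, 38% and 75% of trials (noncentral t, 22.5 per arm).

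**Step 5: can data already collected separate the effects?** Write I for the intervention mean and C for the control mean. Then, exactly,

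I(V3) − C(V3) = [I(V3) − I(V2)] + [I(V2) − C(V3)].

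The second bracket matches the arms on 2 weeks of ToT access. It still differs in time on study and in whether unos.org was open alongside ToT. It is also imprecise. With about 22 per arm, SE = SD × √(1/22 + 1/22) = 0.30 × SD, which is 6.0 points at an assumed SD of 20 and 7.5 at 25. A 95% interval is then roughly ±12 (1.96 × 6.0) to ±15 (1.96 × 7.5) points on the 0-100 scale. An order effect of 5 to 10 points is 0.7 (5/7.5) to 1.7 (10/6.0) standard errors. In SD units it runs from 0.2 (5/25) to 0.5 (10/20), and by the rates in step 4 a significance test would miss it in about 62% to 90% of trials.

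**The case against.** The strongest reply is that the plan makes no wrong statement. The access times in parentheses are correct, the comparison is randomized, and nowhere does the plan say that the difference will be interpreted as an effect of duration. This stands. A reader might infer that the plan asserts a duration effect, but that reading comes from the arm labels together with the stated use of the data, not from an explicit claim.

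The larger trial's duration also does not rest on this contrast alone. The sentence about duration refers to the study data as a whole. The week-4 interview asks directly about ideal time with the site and weighs 4 weeks against 3 months, a range that a 2-versus-4-week contrast could not settle even if unconfounded. Section 1.3.2 plans to relate continued use to preparedness at one month, and 2.6.3 adds the usage models. This also stands, although these sources are observational or qualitative and name no order adjustment.

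A reader might infer that the design already holds the rating needed to separate order from duration, namely the intervention arm at V2 against the control arm at V3. Step 5 shows that it does not. That contrast carries differences of its own, and it is too imprecise for a result near zero to show that order effects are absent.

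A reader might also suppose that contrast between the sites affects only the control arm. By V3 both arms have had both sites open for two weeks, and the week-4 guide asks both to compare them, so ratings in either arm may move. Nor is this a full crossover: the first site is not withdrawn, and what is reversed is the order of first access.

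**Conclusion.** The concern holds as a point of labelling and interpretation. The V3 comparison is a valid randomized contrast of ToT then both sites against unos.org then both sites. It cannot be read as the effect of 4 rather than 2 weeks of ToT, because ToT weeks, order of first access and unos.org weeks (and probably prior rating) are fully aliased. That conclusion follows from the two-sequence design and needs no assumed effect size.

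The size of any distortion is unknown, because the documents give no order effect and no SD. The figures in SD units and points illustrate what an order effect would do; they are not evidence that one exists. Two inferences are used: that the comparison is made at V3, and, for the prior-rating difference and the paired estimate, that the intervention arm's V2 PrepDM refers to ToT.

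Severity is low. This is one secondary endpoint in a pilot of about 50 participants, and the 2-week co-primary comparison precedes the rollover and is unaffected.

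**What to change.** In sections 2.6.1 and 2.6.3:

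1. Name V3 as the visit and describe the comparison as one of access sequences. State that duration, order and unos.org access are not separable in it, and that it will not by itself be used to set the duration of the larger trial.
2. Report the intervention arm's paired change in PrepDM for ToT from V2 to V3, with a 95% CI, as the more direct evidence on whether preparedness is held or raised at one month (the objective in 1.3.2). Confirm which site that arm rates at V2. State that the change is not a randomized contrast and that it includes time on study, repeat rating and the unlocking of unos.org.
3. Optionally show intervention V2 against control V3 descriptively, with a CI. It should not serve as a test that must be passed before duration is discussed, for the reasons in step 5.

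The cost is a few lines of wording and one extra estimate from planned ratings. The downside is a more cautious statement about duration.

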2.6.2 Sample size determination

This will be a pilot and feasibility study, and we anticipate 90% of 50 enrolled participants (95% CI 79-96%) will complete the 2-week study visit (V2).

2.6.3 Statistical analysis plan

Primary endpoints

The co-primary endpoint is feasibility, which will be defined successful by 90% of enrolled participants completing the 2-week study visit (V2). Descriptive statistics will be used to determine whether this threshold was met.

The co-primary endpoint of difference in PrepDM scale score (Difference = intervention – control) at 2-weeks will be assessed using linear regression, with statistical significance level set at 2-sided alpha <0.05.

Secondary endpoints

Continuous secondary endpoints will be assessed using linear regression, with statistical significance level set at 2-sided alpha <0.05.

Categorical secondary endpoints will be assessed using Pearson's chi-squared test of independence, with statistical significance level set at 2-sided alpha <0.05.

Graphical methods and descriptive statistics will be used to evaluate differences in usage during the 4 weeks of access across subsets of the cohort with different socioeconomic

status (based on insurance status, income, education level) and health literacy (based on S-TOFHLA). Exploratory models will test for a dose-response relationship by 1) time spent using the tool (uses/week) and 2) number of ‘CF Stories’ viewed and PrepDM Scale at 2-week and 4-week study visits. Linear regression may be used to determine whether predictors of increased time spent using the tool can be identified from baseline demographics and questionnaire results. Subgroup analyses will compare changes across instruments among participants with adequate health literacy to those with inadequate or marginal health literacy. We will also perform subgroup analysis for patients with $FEV_1 < 30\%$ predicted.

These data will inform the feasibility of completing a larger, multicenter, randomized controlled trial of ToT and will inform duration of the larger trial.

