RATIONALE	
 1. Despite therapeutic advances in CF care, many CF patients will go on to require LTx, including individuals already affected by advanced lung disease, those for whom highly effective CFTR modulators are not available or not tolerated, and for some despite CFTR modulators. Individuals with CF seek information about LTx and feel underprepared for the LTx decision. Use of a decision support tool or online educational materials about LTx may improve the quality, efficiency and effectiveness of LTx education in CF clinic and empower patients to engage in discussions about this complex medical treatment by increasing their sense of preparedness for the discussion. Feasibility must be established. The Preparation for Decision Making (PrepDM) Scale[1] is a validated measure of preparedness for decision making with known variance and high internal consistency (a 0.92-0.96), but it has not been studied in the CF population. Individual questions within the PrepDM Scale are informative and reflect IPDAS process measures[2, 3]. It is unclear whether there are ceiling or floor effects for particular questions within the PrepDM scale when evaluating a LTx decision support tool in the CF population, and the proposed pilot study utilizing a test-retest approach will establish preliminary means standard deviations, and reliability in this population. A prior decision aid for LTx in CF was shown to decrease decisional conflict in a randomized clinical trial and we will assess change in the Decisional Conflict Scale as a secondary endpoint.[4] 2. Engagement with Take on Transplant over time allows users to explore the content, potentially viewing more 'CF Stories', 'Resource Library', and 'Frequently Asked Questions' content and more interactions with 'My CF Stage'. Shared decision-making may naturally appeal to and benefit individuals who seek out health-related information, feel empowered to advocate for their own needs, and have more advanced educational attainment, while potentially increasing disparities for patients who are already disadvantaged. Shared decision making interventions

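### The co-primary PrepDM regression does not name the FEV1 stratum used in the randomisation. If it is fitted with arm alone and the stratum is prognostic, the confidence interval is slightly wider than it need be (minor)

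*Combined protocol and SAP*

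**What the plan says.** - Section 2.5.3 (Allocation to treatment arms): "Participants will be randomized 1:1 to either the intervention" or the attention control, "stratified by $FEV_1 < 30\%$ versus 30-50" per cent. Blocking within strata is not stated.
- Section 2.6.3 (Statistical analysis plan, primary endpoints): the PrepDM difference, intervention minus control, "at 2-weeks will be assessed using linear regression, with statistical significance level set at 2-sided alpha <0.05". No covariate is named. The synopsis and sections 1.3.1 and 2.6.1 describe the endpoint only as an intention-to-treat difference in means and do not supply a stratum term.
- Section 2.6.3, later: "We will also perform subgroup analysis for patients with $FEV_1 < 30\%$ predicted". This is the only place where FEV1 enters the analysis plan.
- Synopsis, Rationale, on the PrepDM Scale: "but it has not been studied in the CF population".
- Sections 2.4.2 and 2.6.2: about 50 enrolled and 45 (90%) expected to complete the 2-week visit. No PrepDM SD, effect size or power is given.

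**The concern.** Stratified allocation is used because the factor is thought to matter for the outcome. When allocation is blocked within strata, the design takes the between-stratum variation out of the arm contrast. A regression on arm alone still counts that variation as residual error, so it reports a standard error larger than the true one. The interval is too wide and the test rejects too rarely under the null. If allocation is not blocked, the arm-only test holds its level, but a prognostic stratum left out of the model costs real precision.

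PrepDM is the only co-primary endpoint with a significance test, and it rests on about 45 people. The question is how much precision the silence in section 2.6.3 could cost.

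**Working it through.** **The plan's own figure.** Section 2.6.2 gives a 95% CI of 79-96% for 90% of 50. The Wilson interval for 45/50 has centre (0.9 + 1.96²/100)/(1 + 1.96²/50) = 0.871 and half-width 0.085, that is 78.6% to 95.7%. The figure reproduces. It concerns completion only.

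**Inputs from the documents.** 1:1 allocation; two FEV1 strata; 50 enrolled and 45 analysed; two-sided alpha 0.05.

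**Assumptions, because the documents are silent.** 30% of participants in the FEV1 <30% stratum; a true arm effect of 0.8 SD; dropout at random; within-arm total SD of 1; stratum R² (share of within-arm PrepDM variance explained) from 0 to 0.20. With stratum share p, the stratum difference is sqrt(R²/(p(1-p))) SD. At p = 0.30, R² = 0.05 gives sqrt(0.05/0.21) = 0.49 SD.

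**Simulation, 20,000 trials per setting.** Half-width is t × mean model SE, with t(0.975, 43) = 2.017 for arm only and t(0.975, 42) = 2.018 with the stratum. The Monte Carlo standard error of one power figure is about sqrt(0.75 × 0.25/20,000) = 0.003. Each cell shows arm only / arm + stratum.

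Blocks of 4 within stratum:

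| R² | Stratum difference (SD) | Half-width (SD) | Power at 0.8 SD | Type I error |
|---|---|---|---|---|
| 0 | 0 | 0.598 / 0.600 | 0.744 / 0.743 | 0.050 / 0.050 |
| 0.02 | 0.31 | 0.599 / 0.594 | 0.745 / 0.750 | 0.048 / 0.050 |
| 0.05 | 0.49 | 0.600 / 0.586 | 0.749 / 0.764 | 0.045 / 0.049 |
| 0.10 | 0.69 | 0.599 / 0.569 | 0.748 / 0.781 | 0.040 / 0.048 |
| 0.20 | 0.98 | 0.600 / 0.536 | 0.765 / 0.832 | 0.031 / 0.050 |

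No blocks (independent 1:1 allocation):

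| R² | Half-width (SD) | Power at 0.8 SD | Type I error |
|---|---|---|---|
| 0 | 0.604 / 0.612 | 0.734 / 0.725 | 0.047 / 0.049 |
| 0.02 | 0.605 / 0.606 | 0.737 / 0.732 | 0.051 / 0.051 |
| 0.05 | 0.605 / 0.597 | 0.733 / 0.748 | 0.049 / 0.048 |
| 0.10 | 0.605 / 0.580 | 0.739 / 0.770 | 0.049 / 0.048 |
| 0.20 | 0.606 / 0.549 | 0.735 / 0.814 | 0.050 / 0.048 |

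**Where the loss sits.** With blocks, the actual sampling SD of the estimate is nearly the same in both models: 0.2915 / 0.2911 at R² = 0.05 and 0.2710 / 0.2671 at R² = 0.20, a difference of at most 1.5%. The reported SE is what goes wrong. At R² = 0.20 the arm-only model reports 0.2974 against a true 0.2710, which is 0.2974/0.2710 = 1.10, or 10% too large. Bias of the arm-only estimate is within 0.006 SD in every setting.

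**Cost if the stratum is not prognostic.** With blocks, the SE rises by about 0.2%. Without blocks it rises by 0.3032/0.2997 = 1.012, or 1.2%, and power falls by about 1 point. Break-even without blocks comes where R² equals the expected squared arm-stratum correlation, about 1/44 = 0.023. That is a stratum difference of sqrt(0.023/0.21) = 0.33 SD.

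**Closed-form check.** With exact balance and n = 45, the ratio of CI widths (adjusted/arm only) is [t(42)/t(43)] × sqrt((1-R²) × 43/42). It gives 1.0125 at R² = 0, 0.987 at 0.05, 0.961 at 0.10 and 0.906 at 0.20, with break-even at 0.025. Here R² is the sample value, which averages about 1/43 = 0.023 even for a factor with no effect. That is why the blocked simulation, indexed by the true R², shows almost no cost at zero.

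**Sensitivity.** With blocks and R² = 0.05, power is 0.749 / 0.765 at a 15% stratum share and 0.745 / 0.763 at 50%. For an arm effect of 0.5 SD at 30% it is 0.375 / 0.392. The picture does not change.

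**The case against.** The strongest reply is that section 2.6.3 is silent, not wrong. It does not say the model is unadjusted, so the wider interval needs two conditions: the team fits arm alone, and the stratum predicts PrepDM. Nothing in the documents shows the second. PrepDM rates how well a resource prepared its user, and a strong link with lung function cannot be presumed. For modest stratum differences the gain is tiny: if the SD were 20 points on the 0-100 scale (an illustration only), the half-width would move from about 12.0 to 11.7-11.9 points. The largest gains need a stratum difference of 0.98 SD, more than the assumed arm effect. The omission errs on the conservative side, no power is claimed, and no decision rule uses the PrepDM p-value. Details of the allocation may also exist outside the public text, since the numbering of section 2.5 has gaps.

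All of this stands, and it limits the weight of the point. It does not remove it. The trial stratifies on FEV1 and singles out FEV1 <30% for a subgroup analysis, yet the subgroup analysis does not adjust the primary contrast. Leaving the covariates open also leaves the primary model to be chosen after the data are seen.

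**Conclusion.** The point holds as a minor under-specification, not a validity error. If the PrepDM model is fitted with arm alone, the estimate is unbiased and type I error is not inflated.

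For a stratum difference of 0.31 to 0.49 SD, adding the stratum changes power at 0.8 SD by about +0.5 to +1.5 points with blocks of 4, and by about -0.5 to +1.5 points without. At 0.98 SD the gain is about 7 to 8 points, but that case should not drive the judgement.

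These sizes rest on the assumed stratum share, effect size, R² range and random dropout. The direction with blocking does not depend on the particular values, provided the stratum is prognostic. Whether it is prognostic is unknown for this population.

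**What to change.** In section 2.6.3, state that the 2-week PrepDM score will be regressed on arm and FEV1 stratum as used at randomisation (<30% versus 30-50%), and that the difference, its 95% CI and the two-sided p-value come from that model.

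The change is one sentence and needs no new data, because the stratum is recorded at randomisation. It uses one degree of freedom, and the worst case is the cost shown above for a non-prognostic stratum. The same term could be used in the between-arm models for continuous secondary endpoints for consistency. No gain has been computed for those, and the point does not depend on them.
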